Appendix 3.3.6 Abnormal Vital Sign Values

Not every vital sign abnormality qualifies as an AE. A vital sign result must be reported as an AE if it meets any of the following criteria:

Is accompanied by clinical symptoms

Results in a change in study treatment (e.g., dosage modification, treatment interruption, or treatment discontinuation)

Results in a medical intervention or a change in concomitant therapy

Is clinically significant in the physician’s judgment

It is the physician’s responsibility to review all vital sign findings. Medical and scientific judgment should be exercised in deciding whether an isolated vital sign abnormality should be classified as an AE.

If a clinically significant vital sign abnormality is a sign of a disease or syndrome (e.g., high blood pressure), only the diagnosis (i.e., hypertension) should be recorded in the AE section of the CRF.

Observations of the same clinically significant vital sign abnormality from visit to visit should only be recorded once in the AE section of the CRF (see Appendix 3.3.4 for details on recording persistent AEs).

Appendix 3.3.7 Abnormal Liver Function Tests

The finding of an elevated ALT or AST ($> 3 \times$ the ULN) in combination with either an elevated total bilirubin ($> 2 \times$ the ULN) or clinical jaundice in the absence of cholestasis or other causes of hyperbilirubinemia is considered to be an indicator of severe liver injury. Therefore, physicians must report as an AE the occurrence of either of the following:

Treatment-emergent ALT or AST $> 3 \times$ ULN in combination with total bilirubin $> 2 \times$ the ULN

Treatment-emergent ALT or AST $> 3 \times$ ULN in combination with clinical jaundice

The most appropriate diagnosis or (if a diagnosis cannot be established) the abnormal laboratory values should be recorded in the AE section of the CRF (see Appendix 3.3.5) and reported to the marketing authorization holder immediately (i.e., no more than

24 hours after learning of the event) either as an SAE or a non-serious AE of special interest (see Section 8.1.3.1).

Appendix 3.3.8 Deaths

All deaths that occur during the protocol-specified AE reporting period (see Section 8.1.2.1), regardless of relationship to study medicine, must be recorded in the AE section of the eCRF and immediately reported to the marketing authorization holder (see Section 8.1.3.1).

Death should be considered an outcome and not a distinct event. The event or condition that caused or contributed to the fatal outcome should be recorded as the single medical concept on the AE section of the CRF. Generally, only one such event should be reported. The term “**sudden death**” should only be used for the occurrence of an abrupt and unexpected death due to presumed cardiac causes in a patient with or without preexisting heart disease, within 1 hour after the onset of acute symptoms or, in the case of an unwitnessed death, within 24 hours after the patient was last seen alive and stable. If the cause of death is unknown and cannot be ascertained at the time of reporting, “**unexplained death**” should be recorded on the AE section of the CRF. If the cause of death later becomes available (e.g., after autopsy), “unexplained death” should be replaced by the established cause of death.

Appendix 3.3.9 Preexisting Medical Conditions

A preexisting medical condition is one that is present at the screening visit for this study. Such conditions should be recorded on the General Medical History and Baseline Conditions in the CRF.

A preexisting medical condition should be recorded as an AE only if the frequency, severity, or character of the condition worsens during the study. When recording such events in the AE section of the CRF, it is important to convey the concept that the preexisting condition has changed by including applicable descriptors (e.g., “more frequent headaches”).

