6.2 POPULATION

The patient population taking part in the study will comprise patients aged ≥ 18 years with untreated advanced FL.

Patients must meet the following criteria for study entry:

1. Signed Informed consent according to local regulations, after performing at least 2 cycles of induction treatment with Obinutuzumab and chemotherapy, within 1 year from beginning of treatment;
2. Age ≥ 18 years;

Patients who meet any of the following criteria will be excluded from study entry:

1. Any contraindications to Obinutuzumab therapy according to local label for specific indication;
2. Concomitant participation in an interventional clinical study;
3. Patients not receiving treatment for untreated follicular lymphoma with Obinutuzumab according to standard of care and in line with the current summary of product characteristics (SmPC)/local labeling

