6.4.2 Data Collected during the Observation Period

During therapy with Obinutuzumab, laboratory assessments are routinely performed in accordance with current guidelines and local standard of care. When performed during the observational period, available results that represent an adverse event in accordance to CTCAE vs. 5, relevant symptom/signal of an event or abnormal laboratory finding that results in a change of the treatment in study will be documented in the eCRF. Most data will be documented during the treatment period when the respective assessments are usually performed according to standard of care. The proposed assessments and suggested timings for assessments in the protocol/observational plan are not mandatory. It is up to the treating physician to perform and document the assessments as performed in the real clinical setting.

In the routine care setting, patients are seen regularly by their treating physicians either for treatment or for regular assessment after treatment. Thus, no study-specific visits or evaluations are required by this protocol.

Tumor assessments collected in eCRF will comprise the following periods as available:

- Baseline tumor assessment
- During induction:
 - Mid induction: tumor assessment performed between cycle 2 and cycle 4 after the start of treatments
 - End induction: tumor assessment performed at the day of cycle 6 /8 (or when induction is early discontinued) until 2 month later
- After induction treatment:
 - 1 year after the start of treatment (from 10 to 14 months after the start of treatment)

- 2 years after the start of treatment (from 22 to 26 months after the start of treatment)
- 3 years after the start of treatment (from 34 to 40 months after the start of treatment)
- 1 year after end of maintenance as applicable
- Any tumor assessment, and the method used that shows disease progression, CR or CRu during induction or maintenance.

The lack of tumor assessments in those periods are not a protocol deviation as clinical practice should be followed.

Since the enrolment of patients into the study will occur after the treatment has already started (Patients included should have performed at least 2 cycles of induction treatment with Obinutuzumab but no later than the completion of 1 year of the treatment with Obinutuzumab), a retrospective data collection is expected.

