8.1.2.1 Adverse Event Reporting Period

Qualified *healthcare professionals (HCPs)* will seek information on AEs at each patient contact. All AEs subject to the collecting and reporting requirements outlined in this protocol, whether reported by the patient or noted by study personnel, will be recorded in the patient's medical record and in the AE section of the eCRF.

Once the patient is enrolled in the study, AEs will be collected during the treatment with Obinutuzumab and until 185 days after the last Obinutuzumab dose or until starting a new anti-cancer therapy (whichever occurs first). It includes available data of adverse events that occurred between start of treatment and enrolment in the study (retrospective data collection)..

After this period, AEs that are believed to be related to prior study drug treatment will be collected and should be notified to the competent authority in the Member State where the reactions occurred or to the marketing authorization holder of the suspected medicinal product, but not to both (to avoid duplicate reporting).

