3.3.1 Adverse events

Adverse events are those with start date beyond or equal to the date of first administration of Obinutuzumab and until 185 days after the last Obinutuzumab dose intake or until starting a new anti-cancer therapy (whichever occurs first). After this period AEs that are believed to be related to prior study drug treatment will be collected.

All adverse events will be assigned to a Preferred Term (PT) and will be classified by primary System Organ Class (SOC) according to the MedDRA thesaurus version 22 or higher. Summary statistical tables including frequency counts and percentages and the number of adverse events will be produced.

Data will be listed by study site, patient number, and study day. Events occurring on or after treatment on Day 1 (treatment-emergent adverse events - TEAEs) will be summarized by mapped term, appropriate thesaurus levels, and NCI CTCAE v5.0 grade. In addition, SAEs, including deaths, will be listed separately and summarized.

AEs leading to treatment discontinuation will be listed.

Infusion related reactions (IRRs) and adverse events of special interest (AESI) will be summarized by descriptive statistics and will be listed.

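### Appendix 3.3.9 ties pre-existing conditions to a screening visit instead of the first dose, so on-treatment events still ongoing at study entry can be filed as medical history

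*Protocol*

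**What the plan says.** Protocol Appendix 3.3.9 gives three linked instructions.

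- Definition: "A preexisting medical condition is one that is present at the screening visit for this study".
- Where it goes: "Such conditions should be recorded on the General Medical History and Baseline Conditions in the CRF".
- When it counts as an adverse event: it "should be recorded as an AE only if the frequency, severity, or character of the condition worsens during the study".

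Protocol 6.2 puts consent "after performing at least 2 cycles of induction treatment with Obinutuzumab and chemotherapy, within 1 year from beginning of treatment". Section 6.4.2 explains the retrospective data collection in the same terms: "Since the enrolment of patients into the study will occur after the treatment has already started".

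The rules on what counts as an adverse event use a different time anchor. SAP 3.3.1, in the same words as Protocol 6.7.2, says: "Adverse events are those with start date beyond or equal to the date of first administration of Obinutuzumab". Protocol 8.1.2.1 says of the reporting period: "It includes available data of adverse events that occurred between start of treatment and enrolment in the study". Appendix 2 note h asks for events before consent to be entered as available. Note k asks for all adverse event data in the records after treatment start. The list of retrospective data in 6.4.2 places the baseline condition before treatment begins.

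**The concern.** The wording of Appendix 3.3.9 suits a study in which screening precedes the first dose. Here entry always follows it. Read literally, a cytopenia that appeared in cycle 2 and has not recovered, or an infection still under way at entry, meets the definition of a pre-existing condition although it began on treatment.

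Two things are at stake.

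- **Safety estimates.** Evaluating safety is a stated objective (Protocol 5.2.2). The events exposed to the rule are those that last until entry, so any loss is selective and runs toward under-counting persistent AEs, SAEs and AESIs. Sites may also resolve the conflict differently, which would add between-site variation caused by recording alone.
- **Covariates.** Protocol 6.7.1 and SAP 3.2 name medical history and comorbidities as covariates in the effectiveness models. If a misfiled event reached those variables, a consequence of treatment would be analysed as a baseline predictor. This is a possibility. The documents do not show that it would happen.

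**Working it through.** The plan states no figure on this point, so the check is a comparison of rules followed by simple arithmetic on the exposed window.

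**1. Apply each rule to one case:** onset after the first dose, still present and stable at entry.

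| Rule | Time anchor | Result |
|---|---|---|
| Appendix 3.3.9 | Screening visit | History; AE only on worsening |
| Protocol 6.7.2, SAP 3.3.1 | First administration | AE |
| Protocol 8.1.2.1 | Treatment start to enrolment is included | AE |
| Appendix 2 notes h and k | Before consent; after treatment start | AE, as available |
| Protocol 6.4.2, retrospective list | Baseline is before treatment | Not a baseline condition |

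The first row contradicts the other four.

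**2. Does any text say which rule prevails?** None does. Section 8.1.2.2 sends sites to Appendix 3 for specific instruction on pre-existing conditions. Section 8.1.1.1 makes the part of the AE definition on new or worsening disease subject to exceptions in Appendix 3. A site could therefore reasonably treat 3.3.9 as the governing text.

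**3. Is the screening visit defined?** Appendix 2 has an enrolment visit and no screening visit, so the anchor of 3.3.9 has no place in the schedule.

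**4. Can the analysis recover a misfiled event?** Not reliably. Note h requires only a preferred term for an event before consent. Section 6.4.2 lists onset date among the additional items for prospective events. No section states that an onset date is collected for medical-history entries. SAP 3.4 plans no sensitivity analyses, and SAP 3.6 plans no handling of missing data.

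**5. How long is the exposed window?**

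- Inputs: entry after at least 2 cycles and within 12 months (6.2); induction of about 6 months, maintenance of about 24, and 42 months in total (6.1); 6 or 8 cycles and the administration days (Synopsis Table 1).
- Administrations before entry, if none is omitted: 3 in Cycle 1 + 1 in Cycle 2 = at least 4.
- Cycle length is not stated. Assuming that 6 to 8 cycles fill about 6 months, two cycles take 2 × 6/8 = 1.5 months to 2 × 6/6 = 2 months.
- Window: about 1.5 to 12 months.
- Share of the observation period: 1.5/42 = 4% to 12/42 = 29%.
- Share of the treatment period (6 + 24 = 30 months): 1.5/30 = 5% to 12/30 = 40%.

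These shares describe the time in which an exposed event can start. They are not the share of events lost.

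**6. Which events are exposed?** Only those that start in the window, are present at entry and do not worsen afterwards. Section 6.7.2 counts each patient once per preferred term, so patient-level incidence falls only if that patient has no other recorded event under the same term.

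**The case against.** The strongest reply is that most of the current text already directs the right outcome. Protocol 6.7.2, 8.1.2.1, notes h and k, and SAP 3.3.1 all call for events after the first dose, and 6.4.2 sets baseline before treatment. In Appendix 2 the adverse event row is marked at the enrolment visit, whereas medical history is marked only under retrospective collection. Because 6.1 counts the 42 months from treatment start, the phrase about worsening during the study could be read to cover the pre-entry period as well. A cycle 2 cytopenia would then qualify as an adverse event. Second malignancies are a named AESI, and note h in the protocol asks for AESIs before consent, so a site has little reason to file one as history. The study is descriptive, and POD24 is not touched by this clause.

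Much of this stands. A reader might infer from 3.3.9 that toxicities ongoing at consent are, as a rule, recorded as history and lost. The documents do not support that, because several sections instruct the opposite. A reader might also want a size, for example a true incidence of 20% (60/300) reported as 10% (30/300). That would require half the events to be ongoing and stable at entry and every site to follow 3.3.9 over the other sections. Neither assumption has a source in the documents.

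The contradiction itself remains. The favourable readings depend on a site combining several sections against an explicit restriction in the appendix to which it has been sent.

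**Conclusion.** Appendix 3.3.9 is wrong as written for this design and contradicts the protocol's own adverse event rules. The result is a risk of misclassification at some sites, toward under-counting events that persist to entry. It is not a uniform exclusion of those events. All of the approximately 300 planned patients enter under the clause, but how many have an affected event cannot be estimated from the documents. The conclusion rests on two readings: that the screening visit falls at or near study entry, since no earlier study visit exists, and that Appendix 3 can be taken as the more specific instruction. The effect on model covariates is possible only. The primary endpoint is unaffected.

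**What to change.** In Appendix 3.3.9:

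- define a pre-existing condition as one present before the first obinutuzumab administration;
- make the test for recording it as an AE whether it worsens after that administration;
- state that a condition with onset on or after the first dose is an adverse event even if it is ongoing at consent.

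This uses the anchor already in Protocol 6.7.2 and SAP 3.3.1 and removes the undefined visit.

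For data already entered, before the final analysis:

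- compare medical-history entries with the first-dose date where an onset date exists, and query the site where it does not;
- move misfiled entries to the adverse event page;
- keep them out of the medical history and comorbidity covariates.

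The cost is a short protocol clarification, a data check and some site queries. The check cannot be fully programmed unless history onset dates were collected, which the documents do not confirm. No new patient assessments are needed. Reported adverse event rates may rise slightly.

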Appendix 3.3.10 Lack of Therapeutic Efficacy

Events that are clearly consistent with the expected pattern of progression of the underlying disease should not be recorded as AEs. These data will be captured as effectiveness assessment data only. In most cases, the expected pattern of progression will be based on standard criteria (i.e. Revised Response Criteria for Malignant Lymphoma [*Cheson et al. 2007*] and the Deauville 5-point scale [*Meignan et al. 2009*]). In rare cases, the determination of clinical progression will be based on symptomatic deterioration. However, every effort should be made to document progression through use of objective criteria. If there is any uncertainty as to whether an event is due to disease progression, it should be reported as an AE. This exception from reporting includes events of disease progression with a fatal outcome which are clearly attributable to disease progression.

Appendix 3.3.11 Hospitalization or Prolonged Hospitalization

Any AE that results in hospitalization or prolonged hospitalization should be documented and reported as an SAE (per the definition of SAE in Section 8.1.1.2), except as outlined below.

The following hospitalization scenarios are not considered to be SAEs:

Hospitalization for respite care

Hospitalization for a preexisting condition provided that all of the following criteria are met:

The hospitalization was planned prior to the study or was scheduled during the study when elective surgery became necessary because of the expected normal progression of the disease.

The patient has not suffered an AE.

Hospitalization solely due to progression of the underlying cancer

The following hospitalization scenarios are not considered to be SAEs but should be reported as AEs instead:

Hospitalization that was necessary because of patient requirement for outpatient care outside of normal outpatient clinic operating hours

Appendix 3.3.12 Overdoses, Misuses, Abuses, Off-Label Use, Occupational Exposure, or Medication Error

Any overdose, misuse, abuse, off-label use, occupational exposure, medication error (including intercepted or potential), or any other incorrect administration of medicine under observation should be noted in the Drug Administration section of the CRF as *Special Situation (SS)*. Any overdose, abuse, misuse, inadvertent/erroneous administration, medication error (including intercepted or potential), or occupational exposure reports must be forwarded to the marketing authorization holder with or without an AE.

Reports with or without an AE should be forwarded to the marketing authorization holder as per non-serious timelines. If the associated AE fulfills the seriousness criteria, the event should be reported to the marketing authorization holder immediately (i.e., no more than 24 hours after learning of the event, see Section 8.1.3.1).

For the purpose of reporting cases of suspected adverse reactions, an occupational exposure to a medicine means an exposure to a medicine as a result of one's professional or non-professional occupation.

Appendix 3.3.13 Quality Defects, Falsified Products and Products Complaints

Reports of suspected or confirmed falsified product or quality defect of a product, with or without an associated AE, should be forwarded to the marketing authorization holder as

per non-serious timelines. If the associated AE fulfills the seriousness criteria, the event should be reported to the marketing authorization holder immediately (i.e., no more than 24 hours after learning of the event, see Section 8.1.3.1).

Appendix 3.3.14 Drug Interactions

Reports of suspected or confirmed drug interactions, including drug/drug, drug/food, drug/device and drug/alcohol, should be forwarded to the marketing authorization holder as per non-serious timelines. If the associated AE fulfills the seriousness criteria, the event should be reported to the marketing authorization holder immediately (i.e., no more than 24 hours after learning of the event, see Section 8.1.3.1).

Appendix 4

EuroQol 5-Dimension Questionnaire, 5-level version (EQ-5D-5L)

Sotto ciascun argomento, faccia una crocetta sulla casella (UNA SOLA) che descrive meglio la sua salute OGGI.

CAPACITÀ DI MOVIMENTO

Non ho difficoltà nel camminare

Ho lievi difficoltà nel camminare

Ho moderate difficoltà nel camminare

Ho gravi difficoltà nel camminare

Non sono in grado di camminare

CURA DELLA PERSONA

Non ho difficoltà nel lavarmi o vestirmi

Ho lievi difficoltà nel lavarmi o vestirmi

Ho moderate difficoltà nel lavarmi o vestirmi

Ho gravi difficoltà nel lavarmi o vestirmi

Non sono in grado di lavarmi o vestirmi

ATTIVITÀ ABITUALI (per es. lavoro, studio, lavori domestici, attività familiari o di svago)

Non ho difficoltà nello svolgimento delle attività abituali

Ho lievi difficoltà nello svolgimento delle attività abituali

Ho moderate difficoltà nello svolgimento delle attività abituali

Ho gravi difficoltà nello svolgimento delle attività abituali

Non sono in grado di svolgere le mie attività abituali

DOLORE O FASTIDIO

Non provo alcun dolore o fastidio

Provo lieve dolore o fastidio

Provo moderato dolore o fastidio

Provo grave dolore o fastidio

Provo estremo dolore o fastidio

ANSIA O DEPRESSIONE

Non sono ansioso/a o depresso/a

Sono lievemente ansioso/a o depresso/a

Sono moderatamente ansioso/a o depresso/a

[figure not shown]
Sono gravemente ansioso/a o depresso/a

Sono estremamente ansioso/a o depresso/a

- Vorremmo sapere quanto è buona o cattiva la sua salute OGGI.
- Questa è una scala numerata che va da 0 a 100.
- 100 rappresenta la migliore salute che può immaginare.
0 rappresenta la peggiore salute che può immaginare.
- Segni una X sul punto della scala per indicare com'è la sua salute OGGI.
- Poi, scriva nella casella qui sotto il numero che ha segnato sulla scala numerata.

LA SUA SALUTE OGGI =

La migliore salute
che può
immaginare

Appendix 5
Functional Assessment of Chronic illness Therapy-Lymphoma
(FACT-Lym), version 4

Sotto abbiamo elencato delle affermazioni ritenute importanti da persone con la sua stessa malattia.

La preghiamo di selezionare la sua risposta in riferimento agli ultimi 7 giorni.

	BENESSERE FISICO	Per niente	Un po'	Abba- stanza	Molto	Moltis- simo
GP1	Mi manca l'energia	0	1	2	3	4
GP2	Ho nausea	0	1	2	3	4
GP3	Ho difficoltà ad occuparmi delle necessità della mia famiglia a causa delle mie condizioni fisiche	0	1	2	3	4
GP4	Ho dolori	0	1	2	3	4
GP5	Mi danno fastidio gli effetti collaterali della cura.....	0	1	2	3	4
GP6	Mi sento male	0	1	2	3	4
GP7	Sono costretto/a a trascorrere del tempo a letto	0	1	2	3	4
<hr/>						
	BENESSERE SOCIALE/FAMILIARE	Per niente	Un po'	Abba- stanza	Molto	Moltis- simo
GS1	Mi sento vicino/a ai miei amici.....	0	1	2	3	4
GS2	La mia famiglia mi sostiene moralmente.....	0	1	2	3	4
GS3	Ho appoggio morale dai miei amici	0	1	2	3	4
GS4	La mia famiglia ha accettato la mia malattia	0	1	2	3	4
GS5	Sono soddisfatto/a della comunicazione nella mia famiglia a proposito della mia malattia.....	0	1	2	3	4
GS6	Mi sento vicino/a al mio compagno/alla mia compagna (o alla persona che mi offre il maggiore appoggio)	0	1	2	3	4
Q1	Indipendentemente dalla sua attività sessuale, la preghiamo di rispondere alla seguente domanda. Se preferisce non rispondere, barri questa casella _ e passi alla prossima sezione.					
GS7	Sono soddisfatto/a della mia attività sessuale	0	1	2	3	4

La preghiamo di selezionare la sua risposta in riferimento agli ultimi 7 giorni.

BENESSERE FUNZIONALE		Per niente	Un po'	Abba- stanza	Molto	Moltis- simo
GF1	Sono in grado di lavorare (si intende anche il lavoro a casa).....	0	1	2	3	4
GF2	Il mio lavoro (si intende anche il lavoro a casa) mi gratifica	0	1	2	3	4
GF3	Riesco a godermi la vita	0	1	2	3	4
GF4	Ho accettato la mia malattia	0	1	2	3	4
GF5	Dormo bene.....	0	1	2	3	4
GF6	Provo ancora piacere nel dedicarmi ad attività di tempo libero	0	1	2	3	4
GF7	Al momento, sono soddisfatto/a della qualità della mia vita	0	1	2	3	4

La preghiamo di selezionare la sua risposta in riferimento agli ultimi 7 giorni.

ULTERIORI PROBLEMI		Per niente	Un po'	Abba- stanza	Molto	Moltis- simo
P2	In certe zone del corpo sento dolore	0	1	2	3	4
LEU1	Mi danno fastidio gli ingrossamenti e i gonfiori che ho in alcune parti del corpo (ad es. collo, ascelle, inguine)	0	1	2	3	4
BRM3	Mi dà fastidio la febbre	0	1	2	3	4
ES3	Ho sudori notturni	0	1	2	3	4
LYM1	Mi dà fastidio il prurito	0	1	2	3	4
LYM2	Ho difficoltà a dormire di notte	0	1	2	3	4
BMT6	Mi stanco facilmente	0	1	2	3	4
C2	Sto dimagrendo	0	1	2	3	4
Ga1	Mi manca l'appetito0	0	1	2	3	4
HI8	Ho difficoltà a concentrarmi	0	1	2	3	4

N3	Ho paura di prendere delle infezioni	0	1	2	3	4
LEU6	Mi preoccupo che possano manifestarsi nuovi sintomi della malattia	0	1	2	3	4
LEU7	Mi sento isolato/a dagli altri a causa della mia malattia o del trattamento	0	1	2	3	4
BRM 9	Ho alti e bassi di umore	0	1	2	3	4
LEU4	Ho difficoltà a fare programmi per il futuro a causa della mia malattia	0	1	2	3	4

Appendix 6

Criteria for Assessment of Tumor Response: standard Cheson criteria and the Deauville 5-point scale

	% Change in sum of diameters of target lesions from nadir				
	CR	PR	MR ^a	SD	PD
% change from baseline	
 • Complete disappearance of all target lesions and all nodes with long axis <10mm. • $\geq 30\%$ decrease in the sum of longest diameters of target lesions (PR) with normalization of FDG-PET 	$\geq 30\%$ decrease in the sum of longest diameters of target lesions but not a CR	$\geq 10\%$ decrease in the sum of longest diameters of target lesions but not a PR (<30%)	<10% decrease or $\leq 20\%$ increase in the sum of longest diameters of target lesions	
 • $>20\%$ increase in the sum of longest diameters of target lesions • For small lymph nodes measuring <15 mm post therapy, a minimum absolute increase of 5mm and the long diameter should exceed 15mm • Appearance of a new lesion
FDG-PET	Normalization of FDG-PET (Deauville score 1-3)	Positive (Deauville score 4-5)	Any	Any	Any
Bone marrow involvement	Not involved	Any	Any	Any	Any
New lesions	No	No	No	No	Yes or No

CR, complete response; CT, computerized tomography; FDG-PET, [18F]2-fluoro-2-deoxy-D-glucose; MR, minor response; PD, progression of disease; PR, partial response; SD, stable disease.

^aA provisional category.
